4.1.2 Utility Objective

The second objective is to quantify and characterize the use of HD Grid and EnSite Precision with HD Wave in the electroanatomical mapping of PersAF or VT in real-world clinical settings.

Use of HD Grid and EnSite Precision with HD Wave will be quantified and characterized through the summary of the following:

- Overall procedure time: defined as time from initial catheter insertion to final catheter removal.
- Radiofrequency (RF) time: defined as duration of time RF energy is delivered
- Fluoroscopy time: defined as total time subject is exposed to fluoroscopy
- Mapping time associated with mapping arrhythmia: defined as the total cumulative mapping time and mapping time for the creation of each map (including any new or retrospective map created with Manual, AutoMap, and TurboMap mapping)
- Number of mapping points collected: defined as total number of mapping points collected for the creation of each map
- Number of mapping points used: defined as the total number of mapping points used in each map
- Number of used mapping points per minute: defined as the total number of mapping points used divided by the relative mapping time
- Substrate characteristics identified: for each type of arrhythmogenic substrate this will be defined as the frequency of substrate type identified in cases that attempted to identify the specific substrate

Clinical Investigation Plan

- Ablation strategy(s) used: defined by both the type of map used to define ablation strategy and the frequency each ablation strategy/target was used by physicians
- Role of HD Wave map relative to along-the-spline map in ablation strategy decision: as assessed by physician survey comparing maps generated with HD Wave electrode configuration to along-the-spline electrode configurations.
- Maneuverability of HD Grid catheter: defined as the ability to maneuver the HD Grid to each specified anatomic location if attempted, the ability to contact cardiac tissue, and the incidence of induced ectopic beats during maneuvering
- HD Grid electrogram quality relative to ablation catheter electrograms: defined as the proportion of electrograms collected with HD Grid that have better quality/less noise than electrograms collected with the ablation catheter at the same cardiac location as assessed by physician survey

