4.1.3 Additional descriptive endpoints

Additional descriptive endpoints include:

- Change in quality of life (QOL) at 6 and 12 months after receiving HD Grid mapping and RF ablation relative to baseline: defined as change in quality of life assessed in validated QOL surveys (EQ-5D and AFEQT for subjects with PersAF, EQ-5D and HADS for subjects with VT)
- Rate of periprocedural and immediate post procedural (48hrs) procedure- or device- related adverse events in all subjects in whom the HD Grid is inserted (regardless of RF energy delivery).
- Rate of procedure- or device-related adverse events and cardiovascular serious adverse events in all subjects in whom the HD Grid is inserted (regardless of RF energy delivery) through 30 days post study procedure.
- Proportion of VT subjects who receive HD Grid mapping and RF energy delivery free from recurrence of sustained monomorphic VT and new or increased dose of class I/III AAD, and free from recurrence of sustained monomorphic VT on or off class I/III AADs at 12-month follow-up outside the blanking period.
- Rate of repeat ablations after study procedure during 12-month follow up defined as proportion of subjects without an additional ablation procedure to treat indicated cardiac arrhythmia (outside blanking period, if applicable).
- For subjects treated for PersAF:
 - Proportion with atypical atrial flutter (AFL) identified during procedure
 - Of those receiving HD Grid mapping and RF ablation for AFL: Utility of HD Grid specific to the identification and treatment of atypical AFL (as defined in section 4.1.2), including role of HD wave relative to along-the-spline maps in identifying ablation target(s), and time of RF application to terminate atypical AFL

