6.2 Procedure Visit

The procedure should be performed according to the IFU of the HD Grid mapping catheter, EnSite Precision™ Cardiac Mapping System, and any other medical devices used during the procedure. Physicians performing electroanatomical mapping and ablations must be qualified operators and trained on the study. Each physician who ablates during a particular case needs to be documented on the Procedure CRF.

The following information will be collected during the Procedure Visit:

- Antiarrhythmic medications- any current class I/III AAD and dose
- Anticoagulant medications
- Subject cardiac rhythm when they enter the EP lab
- Subject cardiac rhythm during mapping
- Mapping and ablation tools used during the procedure
- Procedural characteristics (set up and timing)
- Fluoroscopy time
- Mapping time (total time to collect mapping data and time for each map created/ retrospectively generated)
- Mapping points collected and used for each map created/ retrospectively generated
- Mapping location(s)
- Electrode configuration used for clinical electroanatomical mapping
- Map type(s) (i.e. Voltage, LAT, CFE, etc.)
- AutoMap settings used (if applicable)
- Arrhythmogenic substrate identified
- Field Scaling use
- Standard and HD Wave map comparisons
- Ablation strategy
- AutoMark settings used (if applicable)
- Cardioversions performed during procedure
- Attempt(s) at induction of arrhythmia as applicable before and after RF delivery
- Subject rhythm after completion of procedure

The entire case (procedure) must be recorded and stored on a study-specific USB (password-protected), provided by the Sponsor, and returned within a reasonable timeline to the Sponsor.

Protocol deviations (refer to Section 10.5 for details) that were observed during the procedure, which include any device used off-label during the procedure, will also be recorded at this time.

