6.2.2 Electroanatomical mapping

The HD Grid Mapping catheter must be used with EnSite Precision to generate a baseline electroanatomical map prior to ablation procedure. Complete contact with the cardiac wall should be achieved before collecting data. Mapping will be done per investigator discretion and is recommended to use an HD Wave electrode configuration for catheter set-up (see Appendix V). Additional maps may be created or retrospectively generated using TurboMap per physician standard practice for diagnostic purposes.

For comparison of HD wave and along-the-spline electrode configuration maps, any HD Wave configuration map used during the case should also be generated using the along-the-spline electrode configurations, preferably using TurboMap with the same geometry as baseline map (see Appendix V for details on configuration and transitions between map types). This may be done during the diagnostic procedure as part of standard of care procedure flow for relevant comparisons prior to ablation strategy determination. If not performed during the procedure, this should be performed after completion of the ablation procedure for comparison of maps resulting from different electrode configurations. Similarly, any along-the-spline electrode configuration map used during the procedure should have a comparable HD Wave configuration map generated for comparison.

For the purposes of this protocol, creating a map or mapping, is considered to be the process of collecting electroanatomical data points within heart via movement or positioning of the mapping catheter within the heart.

A retrospective map will be defined as the generation of a map that does not require collection of any new or additional electroanatomical data points but instead reuses already collected mapping data with new point collection or acquisition settings or electrode configurations selected (via TurboMap) or manual alteration of a copied open map.

Information related to each map generated, and comparison of any HD wave and respective along-the-spline maps will be reported on the appropriate CRF.

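### The rating of HD Wave's role in the ablation decision can rest on a comparison map made only after ablation, and the visible plan does not separate the two timings.

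*Combined protocol and SAP*

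**What the plan says.** Section 4.1.2 lists among the utility summaries: "Role of HD Wave map relative to along-the-spline map in ablation strategy decision: as assessed by physician survey comparing maps generated with HD Wave" and along-the-spline configurations. Section 4.1.3 carries a parallel item for subjects mapped and ablated for atypical atrial flutter, this time about identifying ablation targets.

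Section 6.2.2 gives two routes to the second map. The first is optional: "This may be done during the diagnostic procedure as part of standard of care procedure flow for relevant comparisons prior to ablation strategy determination". The second is the fallback: "If not performed during the procedure, this should be performed after completion of the ablation procedure". The map is to be made "preferably using TurboMap with the same geometry as baseline map", which is a preference and not a requirement.

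The step-by-step instructions in Section 6.2.3 again leave the along-the-spline map optional before ablation, for persistent AF, for atypical flutter and for VT.

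Section 6.2 lists the map comparison among the data collected. It also states: "The entire case (procedure) must be recorded and stored on a study-specific USB".

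**The concern.** The endpoint concerns a decision taken at a definite moment. On the fallback route, one of the two maps did not exist at that moment and cannot have influenced the choice. The operator can still compare the two configurations, but that is a different quantity: what the other map would have added, judged in retrospect.

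Section 8 describes the study as unblinded, and Section 6.2.3 has acute success assessed during the same procedure. A rating given on a post-ablation map may therefore be made with the outcome known.

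Section 1.1.1 says that the effect of this catheter and configuration on ablation strategy is unknown. This endpoint speaks directly to that gap. If the two kinds of rating are summarised together, the reported figure cannot be read as a role in the decision. The interim analysis in Section 8.8 covers acute endpoints on HD Wave use at 250 subjects, so a mixed figure could be reported early.

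**Working it through.** The documents give no figure for this endpoint, so there is nothing to reproduce. The check has two parts.

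**1. The sections side by side**

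- *What is measured (4.1.2, 4.1.3):* the role of one map relative to the other in the strategy decision, or in identifying flutter targets.
- *When the second map is made (6.2.2, 6.2.3):* before the decision if the operator chooses, otherwise after ablation is complete.
- *What is collected (6.2, 6.2.2):* the comparison and information on each map. No listed item says whether both maps existed before the decision, or when the survey was answered.
- *How it is summarised (8.2.2, 8.5):* descriptively on available data, with no pre-specified subgroups beyond separate reporting of persistent AF and VT.
- *Measures against bias (3.2):* the timing of the comparison is not mentioned.

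Following the plan as written can therefore yield both kinds of rating, and no visible text separates them.

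**2. What mixing could do (illustration under assumed inputs)**

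Let f be the share of ratings made on a post-ablation comparison map. Let p_pre and p_post be the rates of one rating category in the two groups. Then:

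pooled rate = (1 − f) × p_pre + f × p_post

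shift from p_pre = f × (p_post − p_pre)

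Neither f nor p_post − p_pre is in the documents. Over an assumed range, in percentage points:

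| f | difference ±10 | difference ±20 |
|---|---|---|
| 25% | ±2.5 | ±5 |
| 50% | ±5 | ±10 |
| 75% | ±7.5 | ±15 |

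For comparison with sampling error, assume one rating from each of the 500 planned subjects (Section 3) and use the exact Clopper-Pearson interval named in Section 8.2.2. At a rate of 0.30 the 95% half-width is 4.1 points with n = 500 and 5.9 points with n = 250.

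Worked example with p_pre = 0.30 and f = 50%:

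- p_post = 0.50: pooled = 0.5 × 0.30 + 0.5 × 0.50 = 0.40, or 200/500, 95% CI 0.357 to 0.444.
- p_post = 0.10: pooled = 0.5 × 0.30 + 0.5 × 0.10 = 0.20, or 100/500, 95% CI 0.166 to 0.238.
- Pre-decision ratings alone: 75/250 = 0.30, 95% CI 0.244 to 0.361.

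Both pooled intervals exclude 0.30. Under these assumptions the shift exceeds the sampling error, and the interval gives no sign of it. The endpoints are reported separately for persistent AF and VT, so actual denominators will be below 500 and intervals wider.

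**The case against.** The case on the other side has several parts, and much of it stands.

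- **Pooling is not stated.** A reader might infer that the plan pools the two kinds of rating. No section says so. The case report forms are under separate cover, the table mockups are not supplied, and part of Section 8.1 is redacted. A timing item or a split may exist there. What stands is that the visible text provides none.
- **The endpoint may be meant as a comparison of configurations.** Its definition goes on to describe a survey comparing maps from the two configurations, which a retrospective rating can serve. The survey wording would settle this and is not available. The label still refers to the strategy decision, so the two readings need to be told apart in the report.
- **Another endpoint records what was used.** Section 4.1.2 separately summarises the type of map behind the strategy, and Section 6.2 collects the configuration used clinically. These show which map was used, but not its role relative to the alternative.
- **The map itself may be unaffected.** A TurboMap comparison reuses points already collected, so it can rest on pre-ablation data even when generated later. The problem is then mainly hindsight in the rater. Because TurboMap is only preferred, a newly collected post-ablation map is not excluded.
- **Direction is unknown.** It is tempting to say that hindsight favours HD Wave because the plan recommends it. The documents give no support for a direction.
- **Restricting the endpoint to comparisons made before the first RF delivery would go too far.** Early comparison is optional, so that subset is self-selected. Section 6.2.3 allows further mapping and ablation, including for flutter arising mid-procedure. A comparison can follow the first RF delivery and still precede its own decision.
- **Consequences are limited.** There are no hypothesis tests and no pass/fail criteria, and this is one of twelve utility summaries.

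**Conclusion.** The concern holds in a limited form. The endpoint is worded as a role in a decision, yet the mapping instructions allow it to be rated on a map made after that decision was carried out. Nothing visible records or separates the two situations, so the summary can mix actual role with hypothetical preference.

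The 2.5 to 15 point range is conditional on the assumed shares and differences and is not an estimate for this study. The documents do not support a claim that HD Wave will be flattered, nor a claim that the sponsor intends to pool. What is affected is the interpretation of this endpoint and of the matching flutter item, not error rates or power. It is a cheap improvement worth making, subject to what the unseen forms and mockups contain.

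**What to change.** For each HD Wave/along-the-spline comparison:

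- record, or derive from the case recording already returned to the sponsor, whether both maps were available before the ablation decision to which they relate;
- record whether the survey rating was made before or after that ablation, since an operator who had both maps in time may still have rated them afterwards.

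Keep this per comparison, not per case, so that maps for later decisions are classified correctly.

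In Sections 4.1.2 and 8.2.2, and for the flutter item in 4.1.3, report the ratings separately by this timing and show both groups. Base any statement about the role in the ablation strategy decision on the pre-decision comparisons. Label the post-ablation ones as retrospective configuration comparisons.

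The cost is one or two form fields and smaller denominators per group; no clinical procedure changes. The pre-decision group will be self-selected by site practice, and the report should say so. If the forms or table mockups already capture the timing, the sponsor need only confirm this and state the split in the plan.

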6.2.3 Indication-specific Procedural Recommendations

6.2.3.1 Persistent AF:

Create a baseline geometry and map (at a minimum, collect baseline map, other maps may be collected or retrospectively generated per standard of care) of entire left atrium using HD Grid with HD Wave electrode configuration. Create or retrospectively generate any additional electroanatomical maps (may include generation of maps with along-the-spline configuration, preferably using TurboMap with same geometry; see Appendix V). Use the baseline HD Wave map and/or additional maps as clinically necessary, to identify ablation target(s), and use ablation catheter per IFU to perform ablation per standard of care. Assess acute procedural success. Collect additional maps and perform additional ablation as clinically necessary. Ablation to treat other arrhythmias that occur during the procedure are allowed per physician discretion and standard of care.

If the subject presents in atypical AFL at any time during the procedure or as a result of induction, diagnostic mapping and RF ablation will be allowed. If this occurs, HD Grid with HD Wave electrode configuration should be used to create diagnostic maps per standard of care. Create or retrospectively generate any additional electroanatomical maps (may include generation of maps with along-the-spline configuration, preferably using TurboMap with same geometry; see Appendix V). Use the HD Wave map and/or additional maps as clinically necessary, to identify ablation target(s), and use ablation catheter per

Clinical Investigation Plan

IFU to perform ablation per standard of care. Information related to diagnostic mapping and ablation of the atypical AFL will be collected.

6.2.3.2 VT:

Create a baseline geometry and map (at a minimum, collect baseline voltage map, other maps may be collected per standard of care) of the ventricle(s) using HD Grid with HD Wave electrode configuration. Create or retrospectively generate any additional electroanatomical maps (may include generation of maps with along-the-spline configuration, preferably using TurboMap with same geometry; see Appendix V). Use the voltage HD Wave map, and/or other maps as clinically necessary to identify ablation target(s). Use ablation catheter per IFU to perform ablation per standard of care. Attempt to re-induce any VT ablated if possible. Assess acute procedural success. Create post-ablation voltage map or collect additional maps and perform additional ablation if clinically necessary.

6.3 Pre-discharge Visit (In-hospital)

Prior to discharge after the study procedure, a Pre-discharge visit will be completed. The following information will be collected from each subject at the Discharge Visit:

- 12-lead ECG
- Collect ICD session records and interrogation reports if applicable
- Arrhythmia recurrence
 - For the purposes of this clinical study recurrence of arrhythmia is deemed to have occurred only when the arrhythmia is documented on ICD, ECG, or other monitoring device used per standard of care. Atrial arrhythmias 30 seconds or longer will be collected. Ventricular arrhythmias treated by an ICD, or lasting 30 seconds or longer will be collected
- Antiarrhythmic medications- any current class I/III AAD and dose
- Adverse events if applicable
- Protocol deviations if applicable

6.4 Follow-up Visits

Follow-up visits are scheduled at 6 months and 12 months post procedure. The scheduled visit windows are calculated from the index procedure.

6.4.1 6-month (180 days ± 90 days) and 12-month (360± 90 days) Visits

The 6-month follow-up visit may be completed in-clinic or via phone call per investigational site standard of care. The 12-month follow-up visit must be completed in-clinic. The following information will be collected at each visit:

- Arrhythmia recurrence
- Antiarrhythmic medication- including any current class I/III AAD and dose
- Completion of the EQ-5D/AFEQT (for subjects treated for PersAF) or EQ-5D/HADS (for subjects treated for VT)
- Collect ICD session records and interrogation reports if applicable
- Holter monitoring at 12-month visit (for patients treated for PersAF)
 - *Subjects treated for PersAF will be issued a Holter monitor at the 12-month visit and instructed to obtain a 48-hour recording. A core laboratory will review each recording and report findings to the Sponsor.

Clinical Investigation Plan

- Other monitoring device source documentation of arrhythmia if applicable
- Adverse events if applicable
- Document any cardiovascular healthcare utilization performed since the last scheduled study visit as defined in Section 6.4.3 if applicable
- Protocol deviations if applicable

NOTE: The Sponsor may request access to other patient data during the required protocol follow up visits or throughout the follow up period, which may include, but is not limited to, data from implanted device(s).

Record the required information on the appropriate CRF(s). Documentation of arrhythmia (e.g. ECG printouts, Holter printouts, session records) where applicable, should be retrieved and submitted electronically through EDC to the Sponsor.

Sponsor representatives can be involved in providing support during the follow-up procedures.

6.4.2 Unscheduled Visits

If a subject is seen by any physician for possible arrhythmia recurrence and/or arrhythmia associated symptoms outside of a regularly scheduled study visit and/or had an urgent care or emergency room visit regarding possible arrhythmia, these visits need to be documented as “Unscheduled Visits”. Minimally, the following information should be documented for an unscheduled visit.

- 12-lead ECG, if performed during the visit
- ICD session records and interrogation reports if applicable
- Other monitoring device source documentation of arrhythmia if applicable
- Antiarrhythmic medication- including any current class I/III AAD and dose
- Occurrence of any repeat ablation
- Document adverse events and cardiovascular healthcare utilization if applicable
- Protocol deviations if applicable

6.4.3 Healthcare Utilization Documentation

Healthcare utilization for cardiac-related hospitalizations (inpatient or outpatient), emergency room visits, and/or urgent care visits will be documented in this clinical study. Subjects will be interviewed at each scheduled visit to determine if they had any cardiac-related hospitalizations (inpatient or outpatient), emergency room visits, and/or urgent care visits since their last scheduled visit. Source documentation for these visits should be obtained and a Healthcare Utilization form completed.

6.4.4 Patient Reported Outcome Measures – Quality of Life Questionnaires

The coordinator or designee will administer patient-reported outcome questionnaires. It is important the subject understands the meaning of all words and instructions in the questionnaires. The subject should be instructed to ask any questions about the questionnaires if further explanation is needed. Once the questionnaires are completed, the coordinator or designee will review for completeness to verify that all questions have been answered according to the directions provided.

The following patient-reported outcome measures will be collected for the respective patient populations:

- Persistent AF:
 - EuroQol Five Dimensions Questionnaire (EQ-5D)
 - AF Effect on Quality of Life Survey (AFEQT)
- VT:

Clinical Investigation Plan

- EuroQol Five Dimensions Questionnaire (EQ-5D)
- Hospital Anxiety and Depression Scale (HADS)

